7.1.1.1.1 General Informed Consent

Consent must be documented by the subject's dated signature or by the subject's legally acceptable representative's dated signature on a consent form along with the dated signature of the person conducting the consent discussion.

A copy of the signed and dated consent form should be given to the subject before participation in the trial.

The initial informed consent form, any subsequent revised informed consent form and any written information provided to the subject must receive the IRB/ERC's approval/favorable opinion in advance of use. The subject or his/her legally acceptable representative should be informed in a timely manner if new information becomes available that may be relevant to the subject's willingness to continue participation in the trial. The communication of this information will be provided and documented via a revised consent form or addendum to the original consent form that captures the subject's dated signature or by the subject's legally acceptable representative's dated signature.

Specifics about a trial and the trial population will be added to the consent form template at the protocol level.

The informed consent will adhere to IRB/ERC requirements, applicable laws and regulations and Sponsor requirements.

Protocol/Amendment No.: 001-08

7.1.1.1.2 Consent and Collection of Specimens for Future Biomedical Research

The investigator or qualified designee will explain the FBR consent to the subject, or the subject's legally acceptable representative, answer all of his/her questions, and obtain documented informed consent before performing any procedure related to FBR. A copy of the informed consent will be given to the subject before performing any procedure related to FBR.

7.1.1.2 Inclusion/Exclusion Criteria

All inclusion and exclusion criteria will be reviewed by the investigator or qualified designee to ensure that the subject qualifies for the trial.

7.1.1.3 Subject Identification Card

All subjects will be given a Subject Identification Card identifying them as participants in a research trial. The card will contain trial site contact information (including direct telephone numbers) to be utilized in the event of an emergency. The investigator or qualified designee will provide the subject with a Subject Identification Card immediately after the subject provides documented informed consent. At the time of treatment allocation/randomization, site personnel will add the treatment/randomization number to the Subject Identification Card.

The subject identification card also contains contact information for the emergency unblinding call center so that a health care provider can obtain information about trial medication/vaccination in emergency situations where the investigator is not available.

7.1.1.4 Medical History

A medical history will be obtained by the investigator or qualified designee. Medical history will include all active conditions, and any condition diagnosed within the prior 10 years that are considered clinically significant by the investigator. Details regarding the disease for which the subject has been enrolled in the trial will be recorded separately and should not be listed in the medical history. Smoking history will be obtained.

7.1.1.5 Disease Details

The investigator or qualified designee will obtain prior and current details regarding disease status.

7.1.1.6 Prior Oncology Treatment History

The investigator or qualified designee will record all prior cancer treatments including systemic treatments, radiation, and surgeries.

Protocol/Amendment No.: 001-08

7.1.1.7 Prior and Concomitant Medications Review

7.1.1.7.1 Prior Medications

The investigator or qualified designee will review prior medication use, including any protocol-specified washout requirement, and record prior medication taken by the subject within 28 days before first dose of trial medication. Treatment for the disease for which the subject has been enrolled in this trial will be recorded separately and should not be listed in prior medications.

7.1.1.7.2 Concomitant Medications

The investigator or qualified designee will record medication, if any, taken by the subject during the trial and through the 30-day Safety Follow-up Visit. After the Safety Visit, record all medications related to reportable SAEs and ECIs.

All medications related to reportable SAEs and ECIs should be recorded as defined in Section 7.2 – Assessing and Recording Adverse Events.

7.1.1.8 Assignment of Screening Number

All consented subjects will be given a unique screening number that will be used to identify the subject for all procedures that occur prior to randomization or treatment allocation. Each subject will be assigned only one screening number. Screening numbers must not be re-used for different subjects.

Any subject who is screened multiple times will retain the original screening number assigned at the initial screening visit.

Subjects who crossed over into Arm 2 will retain the original screening number assigned at the initial screening visit. Specific details on the screening visit requirements (screening/rescreening) are provided in Section 7.1.5.1.

7.1.1.9 Assignment of Treatment/Randomization Number

Part I

All eligible subjects will be allocated, by IWRS assignment, and will receive a treatment number. The treatment number identifies the subject for all procedures occurring after treatment allocation. The assigned screening number will become the subjects' treatment number. Once a treatment number is assigned to a subject, it can never be reassigned to another subject.

A single subject cannot be assigned more than 1 treatment number.

This treatment number will be used throughout the protocol for operational purposes. The treatment number will be assigned by IWRS at the time of enrollment. Treatment allocation will be accomplished by nonrandom assignment by IWRS. When more than one treatment arm is open for enrollment, investigator assessment of eligibility, tumor accessibility to IT therapy, location of lesion, as well as presence of a distant discrete measurable lesion that can be biopsied, will determine allocation.

Protocol/Amendment No.: 001-08

Part II

Treatment allocation will be accomplished by nonrandom assignment by IWRS. When more than one cohort is open for enrollment, investigator assessment of tumor histology, eligibility, and lesion accessibility to IT therapy will determine allocation.

7.1.1.10 Trial Compliance (Medication/Diet/Activity/Other)

Interruptions from the protocol specified treatment plan for ≥ 3 weeks require consultation between the investigator and the Sponsor and written documentation of the collaborative decision on subject management.

All doses of MK-1454 and pembrolizumab will be administered under the supervision of a qualified physician and/or designee experienced in the use of anticancer agents.

Instructions for preparing and administering study drugs will be provided in the Procedures Manual.

7.1.1.11 Trial Communication Plan Summary

Safety data from individual subjects will be closely followed by the Principal Investigator and the Sponsor on an ongoing basis and shared at regular safety teleconferences (typically once per week). The safety and tolerability of all subjects, including those undergoing DLT evaluation as well as those who have completed DLT evaluation, will be reviewed prior to the start of the next cohort. The Sponsor and principal investigators will assess the appropriateness of dose escalation and assess safety and tolerability at the completion of each cohort, and prior to the opening of enrollment for the next cohort. The subsequent dose level to be tested in the next cohort of subjects will be communicated to the investigator or designee following each dose escalation decision meeting. A memorandum will be sent to each site to communicate the specified next dose level. Subjects will be enrolled and allocated via IWRS according to the dose escalation and confirmation guidelines outlined in Section 5.2. The dose at each cohort will be specified via IWRS. Cohorts will be opened or closed through IWRS to assure correct dosing in each cohort.

7.1.2 Clinical Procedures/Assessments

7.1.2.1 Adverse Event Monitoring

The investigator or qualified designee will assess each subject to evaluate for potential new or worsening AEs as specified in the Schedule of Activities and more frequently if clinically indicated. AEs will be graded according to NCI CTCAE Version 4. Toxicities will be characterized in terms of seriousness, causality, toxicity grade, and action taken with regard to trial treatment.

All AEs of unknown etiology associated with MK-1454 and pembrolizumab exposure should be evaluated to determine if it is an ECI of a potential immunological etiology (irAE). See Section 7.2.3.2 regarding the identification, evaluation, and management of AEs of a potential immunological etiology.

Protocol/Amendment No.: 001-08

This is a dose escalation trial to establish the MTD of MK-1454 alone and MK-1454 in combination with pembrolizumab. Therefore, each dose escalation will be based on the safety and tolerability experienced by subjects at each dose level. The safety and tolerability of each cohort for the DLT evaluation period will be reviewed prior to the start of the next cohort. The Sponsor and the principal investigators or subinvestigators will review the safety and tolerability of each trial treatment, assess the appropriateness of dose escalation, decide the completion of each cohort, and decide the opening of enrollment for the next cohort. Frequency of these communications will depend on the enrollment of each cohort, as well as any potential new information regarding a safety concern in this trial or other relevant trials.

As a Phase 1 trial, there is no plan for an external safety reviewer. Data from individual subjects will be closely followed on an ongoing basis by the Principal Investigator and the Sponsor.

7.1.2.2 Full Physical Examination

The investigator or qualified designee will perform a complete physical exam during the screening period and at additional time points as defined in the Schedule of Activities (Section 6.0). Clinically significant findings from the screening exam should be recorded as medical history.

A directed physical exam should be repeated according to the frequency defined in the Schedule of Activities (Section 6.0). After the first dose of study treatment, new clinically significant abnormal findings should be recorded as AEs.

7.1.2.3 Vital Signs and Weight

Vital signs include temperature, pulse, respiratory rate, blood pressure, and oxygen saturation (pulse oximetry) at the frequency defined in the Schedule of Activities (Section 6.0).

Weight will be obtained at Screening, at C1D1 of each treatment cycle, at EOT, and at the 30-day Safety Follow-up Visit. Height will be obtained at Screening only.

7.1.2.4 Electrocardiogram

A standard 12-lead ECG will be performed using local standard procedure at Screening, with any clinically significant abnormal findings recorded as medical history.

Additional time points for ECGs are according to the Schedule of Activities (Section 6.0). Clinically significant abnormal findings seen on all ECGs performed after Screening should be recorded as AEs.

7.1.2.5 Eastern Cooperative Oncology Group Performance Status

The investigator or qualified designee will assess the ECOG performance status as the time points specified in the Schedule of Activities (Section 6.0). Additional ECOG testing may be performed as clinically indicated.

Protocol/Amendment No.: 001-08

7.1.2.6 Tumor Imaging and Medical Photography

The initial PET/CT scan or MRI for solid tumor imaging as well as medical photography for cutaneous lesions must be performed within 28 days prior to enrollment, and the site study team must confirm that the subject has measurable disease as defined by RECIST version 1.1, IWG revised criteria, or ISCL criteria to confirm eligibility. In subjects with CTCL, it is recommended that CT and PET scans be performed at screening.

Part I – Dose Escalation and Confirmation

For Arms 1, 2, and 3 (Part I), tumor imaging and/or medical photography should be repeated every 9 weeks for solid tumors or every 12 weeks for lymphomas from the first dose of treatment. For subjects with CTCL, medical photography will be performed at each treatment cycle, however, tumor imaging will be repeated only to document and confirm PR, CR, or PD.

Part II – Expansion Cohorts

For Cohort A (HNSCC) and Cohort B (TNBC), imaging will begin at 9 weeks and occur every 9 weeks thereafter. Imaging for HNSCC should include the head, neck, chest, and abdomen at all timepoints. Imaging of the pelvis is optional.

Solid tumor imaging should be acquired by CT (with PET for CTCL, as clinically indicated). For subcutaneous lesions, imaging by either MRI or CT is to be obtained at screening and at the imaging time points outlined in Section 2 SoA for assessment of response. MRI should be used when CT is contraindicated or for imaging of the brain. The same imaging technique and the same imaging modality with/without the use of contrast should be performed for assessment of response in a subject throughout the trial to optimize visualization of existing and new tumor burden. Tumor imaging schedule is based on **calendar days** from the first drug administration, and will not be postponed due to delays in treatment cycles. Additional tumor imaging and/or medical photography may be performed as clinically indicated.

Please refer to the Site Imaging Manual for detailed instructions regarding tumor imaging and medical photography.

A central imaging vendor will be made available for possible future independent review.

7.1.2.7 Response Assessment

7.1.2.7.1 Immune-related RECIST

RECIST 1.1 will be adapted to account for the unique tumor response characteristics seen in treatment with pembrolizumab and MK-1454. Immunotherapeutic agents such as pembrolizumab may produce antitumor effects by potentiating endogenous cancer-specific immune responses. The response patterns seen with such an approach may extend beyond the typical time course of responses seen with cytotoxic agents and can manifest a clinical response after an initial increase in tumor burden or even the appearance of new lesions. Standard RECIST may not provide an accurate response assessment of immunotherapeutic agents such as pembrolizumab and MK-1454. Immune-related RECIST (irRECIST) is RECIST 1.1 adapted as described below to account for the unique tumor response seen with

Protocol/Amendment No.: 001-08

immunotherapeutics. irRECIST will be used by site investigators to assess tumor response and progression, and to make treatment decisions.

Therefore, RECIST 1.1 will be used with the following adaptations:

If radiologic imaging by local radiology shows initial PD, tumor assessment should be repeated at least 4 weeks later in order to confirm PD, with the option of continuing treatment while awaiting radiologic confirmation of progression, as described below.

If repeat imaging shows <20\% increase in tumor burden compared to nadir, stable, or improved previous new lesion (that may have been identified as the cause for initial PD), and stable/improved nontarget disease (that may have been identified as the cause for initial PD). then PD is not confirmed. Treatment may be continued and will then follow the regular imaging schedule.

If repeat imaging confirms PD due to any of the scenarios listed below, then subjects will be discontinued from study therapy. The initial date of Progression will be recorded as the PD date.

In determining whether the tumor burden has increased or decreased, the investigator should consider all target lesions as well as nontarget lesions. For purposes of this protocol, biopsied lesions will not be target lesions for RECIST 1.1 or irRECIST.

Scenarios where PD is confirmed at repeat imaging:

- Tumor burden increase remains $\geq 20\%$ and at least 5 mm absolute increase compared to nadir
- Nontarget disease resulting in initial PD is worse (qualitative)
- New lesion resulting in initial PD is worse (qualitative)
- Additional new lesion(s) since last evaluation
- Additional new nontarget progression since last evaluation

In subjects who have initial evidence of radiological PD, it is at the discretion of the investigator whether to continue a subject on study treatment until repeat imaging is obtained. This clinical judgment decision should be based on the subject's overall clinical condition, including performance status, clinical symptoms, and laboratory data. Subjects may receive study treatment while waiting for confirmation of PD, if they are clinically stable as defined by the following criteria:

- Absence of symptoms and signs indicating clinically significant progression of disease, including worsening of laboratory values
- No decline in ECOG performance status
- Absence of rapid progression of disease
- Absence of progressive tumor at critical anatomical sites (eg, cord compression) requiring urgent alternative medical intervention

When feasible, subjects should not be discontinued until progression is confirmed. This allowance to continue treatment despite initial radiologic progression takes into account the

Protocol/Amendment No.: 001-08

observation that some subjects can have a transient tumor flare in the first few months after the start of immunotherapy, and still have a subsequent disease response. Subjects who are deemed clinically unstable are not required to have repeat imaging for confirmation of PD.

NOTE: In subjects who discontinue study therapy without documented disease progression, every effort should be made to continue monitoring of their disease status by radiologic imaging every 9 weeks (\pm 7 days) until: (1) the start of new anticancer treatment, (2) disease progression (3) death, or (4) the end of the study, whichever occurs first.

Confirmation of PR and CR is required at least 4 weeks after the initial response assessment of PR and CR.

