MK-1454-001-07	11-AUG-2020	Updated the inclusion criteria for Triple-negative Breast Cancer Expansion Cohort to include anti-PD-1/PD-L1 refractory subjects and to add an upper limit for LDH for this cohort, removed the requirement for having a second lesion for biopsy in the Expansion Cohorts, added itRECIST as an exploratory objective, and updated the contraception requirements.
MK-1454-001-06	23-AUG-2019	Documented the Recommended Phase 2 Dose (RP2D) to be used in Expansion Cohorts A and B.
MK-1454-001-05	03-JAN-2019	Updated inclusion criteria for Cohort A at the request of the United States (US) Food and Drug Administration (FDA), to allow the inclusion of subjects with head and neck squamous cell carcinoma (HNSCC) Stage III, IVa, IVb, and IVc disease per TNM Staging AJCC Eighth Edition.
MK-1454-001-04	04-OCT-2018	Designated Dose Escalation and Confirmation phase (Arms 1, 2, and 3) as Part I and updated sections accordingly. Added Expansion phase with 3 Expansion Cohorts (Cohorts A to C) as Part II of the study and added new subsections to describe design, entry criteria, dosing schedule, flow chart, and statistical analysis for the Expansion Cohorts in order to evaluate the safety and tolerability of MK-1454 intratumoral (IT) in combination with pembrolizumab in specific cancer tumor types. Updated sample size, secondary/exploratory objectives, treatments, and schedule of activities to reflect addition of the Expansion Cohorts. Revised the dose escalation and confirmation rules for Arm 3 to include an accelerated titration design (ATD) phase starting at of MK-1454. Visceral IT dosing will increase in frequency and escalate dose b subject tolerance per modified toxicity probability interval (mTPI) design. This change was based on an FDA request to start visceral IT dosing in combination with pembrolizumab at the No observed adverse effect level (NOAEL) dose of

MK-1454-001-08 Final Protocol 27-Jul-2021 Confidential

Document	Date of Issue	Overall Rationale
MK-1454-001-03	09-MAR-2018	Updated protocol sections to add rationale, background, entry criteria, schedule of activities, and procedures for Arm 3 for intratumoral (IT) injection of MK-1454 into visceral lesions in combination with pembrolizumab treatment in order to allow inclusion of subjects with visceral lesions to be treated by IT injection. Updated the objectives, inclusion criteria, schedule of activities, and response assessment criteria for subjects with cutaneous T-cell lymphoma (CTCL).

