2.1.2 Part II – Expansion Phase

Initiation of Expansion Cohorts will be staggered based on emerging safety and tolerability data from Part I. Unless deemed medically unsafe by the investigator, all subjects will be required to undergo a biopsy of the lesion to be injected with MK-1454 during the screening period (prior to MK-1454 administration). Subjects with an amenable lesion at the injected site will also undergo tumor biopsies on Cycle 2 Day 1 and optionally on Cycle 3 Day 1, unless deemed medically unsafe by the investigator. The expansion phase of the trial (Figure 3) will evaluate MK-1454 in combination with pembrolizumab 200 mg IV in the following populations:

- Cohort A: Subjects with HNSCC who are anti-PD-1/PD-L1 refractory
- Cohort B: Subjects with either anti-PD-1/PD-L1 treatment-naïve or refractory unresectable locally advanced or metastatic TNBC
- Cohort C: Subjects with other anti-PD-1/PD-L1 treatment-naïve solid tumors with liver metastases

Cohorts A and B will begin at the preliminary RP2D from Arm 2. MK-1454 IT will be administered from Cycle 3 and beyond, in combination with pembrolizumab 200 mg IV Q3W beginning on C1D1). The RP2D dose and the dose for expansion is confirmed to be MK-1454, administered intratumorally to a minimum of 1 lesion per subject per treatment day and a maximum of 3 lesions per subject per treatment day, in combination with pembrolizumab IV.

Cohorts A and B will initiate prior to initiation of Cohort C.

Cohort C will begin at the preliminary RP2D and frequency established from Arm 3.

Treatment duration in each cohort in Part II will be up 35 cycles (approximately 2 years).

Cohorts A and B will each enroll a maximum of 30 subjects, while Cohort C will enroll up to 60 subjects, for a total of up to 120 subjects in the expansion phase. The 60 Cohort C subjects will be enrolled with approximately 15 non-MSI-H CRC subjects, 15 pancreatic ductal adenocarcinoma subjects, and 30 subjects without these specific diagnoses.

Protocol/Amendment No.: 001-08

The trial will be conducted in conformance with GCP.

AEs will be evaluated according to criteria outlined in the NCI CTCAE v4.

[figure not shown]
Specific procedures to be performed during the trial, as well as their prescribed times and associated visit windows, are outlined in the Schedule of Activities - Section 6.0. Details of each procedure are provided in Section 7.0 – Trial Procedures.

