5.1.3 Subject Inclusion Criteria for Part II - Expansion Cohorts

- 1. Be ≥ 18 years of age on day of signing informed consent.
- 2. Voluntarily agreed to participate by providing documented informed consent. The subject may also provide consent for Future Biomedical Research. However, the subject may participate in the main trial without participating in Future Biomedical Research.
- 3. Have at least one measurable lesion which is amenable to injection. Tumor lesions situated in a previously irradiated area are considered measurable if progression has been demonstrated in such lesions. Intratumoral injection for cutaneous lesions may be performed via visual inspection. Intratumoral injection for subcutaneous lesions may be performed via ultrasound guidance or via palpation. This injectable lesion must meet one of the following criteria:
 - A cutaneous or subcutaneous lesion ≥1 cm in longest diameter for solid tumors, or ≥1.5 cm in short axis for a nodal lesion in solid tumor subjects. The longest diameter for an injectable lesion must be ≤10 cm for both solid tumors and nodal lesions in solid tumor subjects.
 OR
 - Multiple coalescing, superficial lesions which in aggregate have a longest diameter of ≥ 1 cm and ≤ 10 cm.

Protocol/Amendment No.: 001-08

4. In subjects to be treated by liver IT injection, has metastatic liver involvement that does not exceed one-third of the total liver volume. Hepatocellular carcinoma subjects are excluded from eligibility for intratumoral liver injection. In addition, has at least one injectable liver lesion that meets both the following conditions:

- The injectable liver lesion is amenable to image-guided intratumoral injection and biopsy via ultrasound guidance or cross-sectional imaging (CT/MRI). AND
- Injectable lesion(s) must be ≥1 cm in longest diameter and ≤10 cm in longest diameter.
- 5. Subjects with any one of the following solid malignancies who meet all listed conditions of eligibility for an expansion cohort:
 - Cohort A: HNSCC of the oral cavity, oropharynx, hypopharynx, or larynx; anti-PD-1/PD-L1 refractory (see Table 2) metastatic or recurrent. Subjects may not have a primary tumor site of the nasopharynx (any histology).

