Protocol/Amendment No.: 001-08

Trial Period	Screening			MK-1		ycle =	CCI			W; or Q3V Days	V	
	Screening										Cycle 4	
											and	
Cycle			Cycle	1	C	ycle 2	2		Cycl	e 3	Beyond	Notes
Scheduling Day	-28 to -1	1	8	15	1	8	15	1	8	15	1	
Scheduled Window		±3	±3	±3	±3	±3	±3	±3	±3	±3	±3	

a) The observation period may be extended at the discretion of the investigator, per local IRB/IEC, and/or Health Authority mandate.

- b) Up to 2 additional serum samples may be collected if deemed medically necessary (eg. in the setting of an AE).
- c) This sample will be drawn for genetic variations in ADME and planned analysis of the association between genetic variants in DNA and drug response. If the IRB/IEC does not approve of the planned analysis of the association between DNA variation and drug response, or if there is a local law or regulation prohibiting the same, then data analysis will be limited to investigate ADME genetic variations. If the sample is collected, leftover extracted DNA will be stored for FBR if the participant (or their legally acceptable representative) provides documented informed consent for FBR. If the planned genetic analysis is not approved, but FBR is approved and consent is given, then this sample will be collected for the purpose of FBR.
- d) All subjects will be required to provide a sample biopsy of the tumor to be injected with MK-1454 and, if available, a sample biopsy from a distant, discrete noninjected site (at least 2 biopsies at each site), unless deemed medically unsafe by the investigator. For the tumor lesion intended for treatment with IT administration of MK-1454, the sample will be obtained by either punch biopsy for cutaneous lesions, or ultrasound guided biopsy for subcutaneous lesions. If available, for distant, discrete tumor lesions that are not intended for IT administration with MK-1454, the sample biopsy will be obtained by punch biopsy for cutaneous lesions, ultrasound guided biopsy for subcutaneous/visceral lesions, or image-guided biopsy, such as CT-guided biopsy, for visceral and deeper tumor lesions. Method of biopsy will be per guidance of the investigator as well as discussion with the Sponsor. Instructions for tissue collection, processing, and shipment are provided in the Procedures Manual. Leftover main study tissue will be stored for FBR if the subject consents to FBR. Instructions for tissue collection, processing, and shipment are provided in the Procedures Manual.

Protocol/Amendment No.: 001-08

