7.1.3.2.4 Tumor Biopsy

Tumor samples will be collected at the time points described in Section 6.0 – Schedule of Activities.

All subjects will be required to provide a sample biopsy of the tumor to be injected with MK-1454 and a sample biopsy from a distant, discrete noninjected site (if feasible) (at least 2 biopsies at each site) after IT administration of MK-1454, unless deemed medically unsafe by the investigator. For Part II Expansion Cohort, only the injected tumor biopsy is required,

^a Perform on WOCBP only. If urine pregnancy results cannot be confirmed as negative, a serum pregnancy test will be required.

^b Absolute or % acceptable per institutional standard

^c For subjects with a baseline calculated creatinine clearance that is below the normal institutional laboratory range, a baseline measured creatinine clearance should be performed. GFR can be used in place of creatinine clearance.

^d HNSCC or other SCC subjects only

^e BUN is preferred; if not available urea may be tested

Protocol/Amendment No.: 001-08

unless deemed medically unsafe by the investigator. The noninjected lesion should be measurable as defined by RECIST 1.1. Tumor dimensions must be ≥1 cm in longest diameter for non-nodal lesions, or ≥ 1.5 cm in short axis for nodal lesions.

Tumor biopsies will only be performed at tumor sites that are deemed medically safe, in accordance with local guidelines. Sponsor selection criteria for the MK-1454 FIH study assured selection of sites that had investigative staff that were highly experienced in tumor biopsies.

For subjects with lymphoma, only those subjects that have superficial lesions amendable to intratumoral injection will be eligible (cutaneous lesions injected via visual inspection, and subcutaneous lymph nodes injected via ultrasound guidance or palpation). No lymphoma subjects with exclusively deep lymph nodes will be included in this study. Lymphoma subjects who have both superficial and deep lymph nodes will be eligible for enrollment into this study, however only the superficial lymph nodes will be injected.

A predose tumor biopsy will be performed at screening on both the tumor lesion which is intended for treatment with IT injection of MK-1454, as well as on the distant lesion which is not intended for IT injection with MK-1454. For Part II Expansion Cohort, only the injected tumor biopsy is required, unless deemed medically unsafe by the investigator.

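### In Part II a subject whose only measurable lesion is biopsied has no permitted target lesion and cannot score PR, yet still counts in the ORR denominator and the futility check

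*Combined protocol and SAP*

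**What the plan says.** **Target lesions.** Section 7.1.2.7.1 says that, for this protocol, "biopsied lesions will not be target lesions for RECIST 1.1 or irRECIST". Section 4.2.3.1, in the endpoint rationale, is softer: it advises that a designated target should preferably not be core or punch biopsied.

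**Entry to Part II.** Section 5.1.3, item 3: "Have at least one measurable lesion which is amenable to injection". No second lesion is asked for. For liver injection, item 4 continues: "In addition, has at least one injectable liver lesion that meets both the following conditions".

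**Biopsy in Part II.** Section 2.1.2: "Unless deemed medically unsafe by the investigator, all subjects will be required to undergo a biopsy of the lesion to be injected with MK-1454". This applies during screening. The same section adds: "Subjects with an amenable lesion at the injected site will also undergo tumor biopsies on Cycle 2 Day 1". Section 7.1.3.2.4 confirms which lesion is meant: "For Part II Expansion Cohort, only the injected tumor biopsy is required, unless deemed medically unsafe by the investigator". The footnote on tumor biopsy in 6.2.1 asks for "at least 2 biopsies at each site".

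**Scoring and counting.** ORR is the proportion with confirmed CR or PR (8.4.1), by investigator under RECIST 1.1, and 8.9.2 calls it the key efficacy endpoint for Part II. Appendix 12.4 (text to Figure 5) says nontarget lesions are judged as in RECIST 1.1: complete response, unequivocal progression, or neither. The FAS requires measurable disease on the baseline scan and a dose (8.5.3). Evaluability for futility requires one postbaseline imaging assessment (8.7). Neither asks for a target lesion.

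**The concern.** Each rule is reasonable alone. Together they create a subject who meets every entry criterion, is dosed, is scanned and is counted, but for whom one of the two ways to be a responder is closed. Measurable disease at baseline admits the subject to the denominator; the biopsy then removes the only lesion on which a partial response could be measured.

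The error goes one way. Under 7.1.2.7.1 a real partial response in such a subject is recorded as non-response, so the scored ORR can only be at or below the true one. Cohorts A and B have 30 subjects each, so one responder is worth 3.3 percentage points. The first futility look asks whether there is any responder at all among about 15 subjects, which makes it sensitive to a single lost response.

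The SAP handles the parallel problem elsewhere. In 8.4.1 the ORR for noninjected lesions is restricted to participants who had a noninjected target lesion at baseline. The main ORR has no such restriction and no rule for a subject without a target lesion.

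**Working it through.** **1. Reproduce the plan's figures (8.7, true rate 10%).**
- At least 1 of 15: 1 − 0.9^15 = 0.794; the plan says 80%.
- At least 2 of 30: 1 − 0.9^30 − 30 × 0.1 × 0.9^29 = 0.816; the plan says 82%.

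Both reproduce to within a point. They assume that every counted subject can be scored as a responder.

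**2. Follow one subject.** One measurable injectable lesion: eligible (5.1.3, item 3). Lesion biopsied at screening: required unless unsafe (2.1.2, 7.1.3.2.4). Lesion as target: barred (7.1.2.7.1). All disease is then nontarget, so the possible results are CR, progression, or neither (12.4). FAS: included (8.5.3). Futility count: included after one scan (8.7). The chain breaks if the biopsy is waived or if there is another measurable lesion that is not biopsied.

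**3. Effect per affected subject.** Assume a true ORR of 10% in everyone and all responses PR. With k affected subjects:
- expected scored responders in 30 = 0.1 × (30 − k)
- chance of 0 of 15, with k among the first 15 = 0.9^(15 − k)

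| k | Expected responders in 30 | Chance of 0 of 15 |
|---|---|---|
| 0 | 3.0 | 20.6% |
| 1 | 2.9 | 22.9% |
| 2 | 2.8 | 25.4% |
| 3 | 2.7 | 28.2% |

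If a share c of responses is CR, each affected subject costs 0.1 × (1 − c) responders: 0.08 at c = 20%, 0.05 at c = 50%.

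**4. The same as a share f of subjects (f is not in the documents).** Scored rate p = 0.10 × (1 − f), all responses PR; chance of 0 of 15 = (1 − p)^15.
- f = 5%: p = 9.5%; 0 of 15 has chance 22.4%; 2.85 expected responders in 30.
- f = 20%: p = 8.0%; 28.6%; 2.4.

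For Cohort C, only if one liver lesion suffices for entry, the chance of at least 2 of 30 falls from 81.6% to 79.2% (f = 5%) or 70.4% (f = 20%).

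**5. The opposite error.** Suppose the biopsied sole lesion were kept as a target, and a share q of true non-responders with such a lesion then falsely reached PR. The ORR would rise by 0.9 × f × q, against a loss of 0.10 × f under the bar. These are equal at q = 0.10 / 0.9 = 11.1%, whatever f is. The documents give no value for q, so they do not show which rule is less biased.

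**6. What a side-by-side report would show.** Illustration with 6 of 30 subjects affected and 3 responders among the other 24: 3/30 = 10.0% (Clopper-Pearson 95% CI 2.1 to 26.5) against 3/24 = 12.5% (2.7 to 32.4).

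**The case against.** The best case for leaving the plan alone has four parts.

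*The effect is small.* One affected subject costs a tenth of a responder, and the interval around 3/30 runs from 2.1% to 26.5%. ORR is a secondary endpoint in a Phase 1 trial whose primary objective is safety and dose. This stands and limits the severity. It does not remove the bias, which has a known direction and is cheap to expose.

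*The bar is deliberate and conservative.* A lesion as small as 1 cm, sampled at least twice at screening and again at Cycle 2 Day 1, may shrink or measure poorly because of the biopsy. This stands too. It is why the point does not ask for the bar to be reversed.

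*The Site Imaging Manual may cover the case.* Section 7.1.2.6 refers sites to it for detail. It is not among the documents, so this is open. The protocol text would still need to agree with it.

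*Futility is non-binding.* Correct: 8.7 looks at the totality of data, so no cohort stops automatically.

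Two stronger readings are tempting, and the documents do not support them. A reader might infer that three sections conflict and none governs. But 7.1.2.7.1 is the operative rule, and 4.2.3.1 is planning advice that pulls the same way with less force. Appendix 12.4 describes itRECIST, which is exploratory and does not mention biopsy there. It asks for one to five injected and also one to five noninjected targets, which a sole-lesion subject cannot meet. A reader might also infer from the Document History entry for amendment 07, which "removed the requirement for having a second lesion for biopsy in the Expansion Cohorts", that sole-lesion subjects were intended. The entry concerns a second lesion for biopsy; it is consistent with one-lesion entry but does not show that it was the aim.

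**Conclusion.** The gap is real on the current text and should be fixed. Under the plan as written, a Part II subject whose only measurable lesion is biopsied cannot contribute a PR but is counted as a non-responder, so the ORR is understated.

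Scope: clearly Cohorts A and B. For Cohort C, items 3 and 4 of 5.1.3 read together could require a second lesion for liver-injected subjects, and the text does not settle this. Subjects with a waived biopsy or another unbiopsied measurable lesion are not affected.

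The per-subject sizes rest on a true ORR of 10% and on all responses being PR; they shrink in proportion to the share of CRs. The number of affected subjects is unknown, so the total bias in any cohort cannot be stated. The result is a misleading estimate or futility signal. The documents do not support going further to a wrongly stopped cohort, or to a finding that the biopsied lesion ought to be kept as a target.

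**What to change.** 1. In 7.1.2.7.1, state how a subject is scored when the only measurable lesion is biopsied, so that the rule fits the entry criterion in 5.1.3 and the biopsy requirement in 2.1.2 and 7.1.3.2.4. Bring the wording of 4.2.3.1 into line. Either choice carries a bias: the present bar pulls ORR down, and keeping the lesion as a target may push it up.
2. Whichever rule is chosen, flag these subjects in the CRF at baseline.
3. In 8.6.1 and 8.7, report each cohort's ORR, and the responder count at each futility look, twice: in all FAS or evaluable subjects, and excluding the flagged subjects. The second line describes a subset, so it should accompany the main estimate and not replace it. The noninjected-lesion ORR in 8.4.1 already conditions on a baseline target lesion in this way.
4. State in 5.1.3 whether a Cohort C subject may enter on a single liver lesion.

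The cost is a few sentences, one CRF flag and one extra ORR line per cohort. No dosing, biopsy or enrolment rule needs to change for the scoring and reporting steps.
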